## 6.5. Efficacy Analysis

Efficacy analyses will be performed using the FAS, mITT, mITT1 and PP Set for Efficacy. The mITT1 Set is the primary analysis set for efficacy analysis of cases starting from 14 days after first dose, and PP Set for Efficacy is the primary analysis set used in the efficacy analyses for cases starting 14 days after second dose, unless otherwise specified. Subjects will be included in the treatment group which they were randomized.

**Baseline SARS-CoV-2 status** is described in [Section 6.1](#). Baseline SARS-CoV-2 status, the serology test results based on *Roche Elecsys* assay at baseline, the RT-PCR test results at baseline will be summarized by treatment group.

Participants with baseline positive or missing SARS-CoV-2 status will be excluded from the PP Set for Efficacy.

In this study, the serology test results based on Roche Elecsys assay and the RT-PCR test results will be summarized by visit.

### 6.5.1. Endpoint Definition/Derivation

#### 6.5.1.1. Derivation of SARS-CoV-2 Infection

This is a secondary efficacy endpoint, which is a combination of COVID-19 and asymptomatic SARS-CoV-2 infection for participants with negative SARS-CoV-2 status at baseline: the incidence of SARS-CoV-2 infection counted starting 14 days after the second dose of IP will be summarized by treatment group. SARS-CoV-2 infection will be defined in participants with negative SARS-CoV-2 at baseline:

- bAb level against SARS-CoV-2 nucleocapsid protein negative (as measured by *Roche Elecsys*) at Day 1 that becomes positive (as measured by *Roche Elecsys*) counted starting at Day 57 or later, OR
- Positive RT-PCR counted starting 14 days after the second dose of IP.

During the analysis, documented infection is counted starting 14 days after the second dose of IP, which requires positive serology test result based on bAb specific to SARS-CoV-2 nucleocapsid at Day 57 visit or later, or a positive RT-PCR result starting 14 days after the second dose of IP. Derivation of this secondary efficacy endpoint is summarized in Table 2 below.

**Table 2. Derivation for SARS-CoV-2 Infection**

Baseline SARS-CoV-2 Status	Post-baseline assessments		Endpoint: SARS-CoV-2 infection
	PCR test post baseline	bAb levels against SARS-CoV-2 Nucleocapsid	
Negative at Baseline	Positive (either at scheduled NP swab test, or at symptom-prompt NP swab test)		Case
Negative at Baseline		Positive (at scheduled Day 57 visit or later) as measured by Roche Elecsys	Case

The date of documented infection will be the earlier of:

- Date of positive post-baseline RT-PCR result, or
- Date of positive serology test result based on bAb specific to SARS-CoV-2 nucleocapsid

The time to the first SARS-CoV-2 infection will be calculated as:

Time to the 1st SARS-CoV-2 infection = Date of the 1st documented infection – Date of randomization + 1.

Cases will be counted starting 14 days after the second injection, i.e. date of documented infection – Date of the 2nd injection  $\geq$  14.

SARS-CoV-2 infection cases will also be summarized based on tests performed at least 14 days after first dose of IP.

#### **6.5.1.2. Derivation of Asymptomatic SARS-CoV-2 Infection**

This is a secondary efficacy endpoint: the incidence of asymptomatic SARS-CoV-2 infection measured by RT-PCR and/or serology tests obtained at post-baseline visits counted starting 14 days after the second injection in participants with negative SARS-CoV-2 status at baseline.

Asymptomatic SARS-CoV-2 infection is identified by absence of symptoms and infections as detected by RT-PCR or serology tests. Specifically:

- Absence of COVID-19 symptoms
- AND at least one from below:
  - bAb level against SARS-CoV-2 nucleocapsid protein negative (as measured by Roche Elecsys) at Day 1 that becomes positive (as measured by Roche Elecsys) counted starting at Day 57 or later, OR
  - Positive RT-PCR test at scheduled or unscheduled/illness visits

The date of documented asymptomatic infection is the earlier date of positive serology test result based on bAb specific to SARS-CoV-2 nucleocapsid due to infection, or positive RT-PCR at scheduled visits, with absence of symptoms.

The time to the asymptomatic SARS-CoV-2 infection will be calculated as:

Time to the asymptomatic SARS-CoV-2 infection = Date of asymptomatic SARS-CoV-2 infection test – Date of randomization + 1.

Asymptomatic SARS-CoV-2 infection cases will also be summarized based on tests performed at least 14 days after first dose of IP.

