#### **4.1.1.1. Part 1A, the Blinded Phase**

The Blinded Phase of this study is a randomized, observer-blind, placebo-controlled study intended to infer the effectiveness of mRNA-1273 in an adolescent population aged 12 to < 18 years. The study includes 2 arms: (i) 100 µg of mRNA-1273, and (ii) placebo.

[figure not shown]
Approximately, 3000 participants 12 to < 18 years of age will be randomly assigned in a 2:1 ratio to receive mRNA-1273 (n=2000) or placebo (n=1000).

The schematic of study arms and major study events for Part 1A is illustrated in [Figure 2](#) and the Schedule of Assessments is provided in [Appendix E](#).

The goal of the study is to seek an indication for use of mRNA-1273 (100 µg IM, given as 2 injections, 28 days apart) in the 12 to < 18 years age group. Each participant will receive one injection of mRNA-1273 or placebo on Day 1 and Day 29 and then be followed up for a total of 12 months following the second injection.

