#### **6.5.1.2. Derivation of Asymptomatic SARS-CoV-2 Infection**

This is an exploratory efficacy endpoint: the incidence of asymptomatic SARS-CoV-2 infection measured by RT-PCR and/or serology tests obtained at post-baseline visits counted starting 14 days after the second injection of mRNA-1273 in long-term (including Part 1B), and cases counted starting 14 days after the booster dose of mRNA-1273 in Part 1C-1, in participants with negative SARS-CoV-2 status at baseline of each part.

Asymptomatic SARS-CoV-2 infection is identified by absence of symptoms and infections as detected by RT-PCR or serology tests. Specifically:

- Absent of COVID-19 symptoms
- AND at least one from below:
  - bAb level against SARS-CoV-2 nucleocapsid protein negative (as measured by Roche Elecsys) at baseline of each part that becomes positive (as measured by Roche Elecsys) post-baseline, OR
  - Positive RT-PCR test post-baseline (at scheduled or unscheduled/illness visits)

The date of documented asymptomatic infection is the earlier date of positive serology test result based on bAb specific to SARS-CoV-2 nucleocapsid due to infection, or positive RT-PCR at scheduled visits, with absence of symptoms.

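### Asymptomatic SARS-CoV-2 infection can be diagnosed by an unscheduled RT-PCR but not dated by one, so some cases have no documented date and others are dated late (Section 6.5.1.2 of both SAPs)

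*SAP*

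**What the plan says.** In the Part 1A SAP, Section 6.5.1.2 gives two routes by which a participant without COVID-19 symptoms becomes a case:

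- nucleocapsid seroconversion, "counted starting at Day 57 or later, OR"
- "Positive RT-PCR test at scheduled or unscheduled/illness visits"

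The paragraph that follows sets the case date as the earlier of the positive serology and "positive RT-PCR at scheduled visits, with absence of symptoms". Incidence is "counted starting 14 days after the second injection in participants with negative SARS-CoV-2 status at baseline". The time-to-event formula in the same section refers to the date of an infection test without saying which test.

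The SAP for Parts 1B, 1C, 2 and 3 repeats the pattern in its own Section 6.5.1.2. The case route is "Positive RT-PCR test post-baseline (at scheduled or unscheduled/illness visits"), while the date sentence is again limited to scheduled visits.

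The overall infection endpoint (Section 6.5.1.1 of the Part 1A SAP) has no such limit. One of its two candidate dates is the "Date of positive post-baseline RT-PCR result", whatever the visit type, and the earlier of the two applies.

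**The concern.** A test that is enough to make a participant a case should also be able to date the case. Here it cannot if the swab was unscheduled. Three things depend on the date: whether the case falls 14 days or more after dose 2, how much person-time the participant contributes (Section 6.5.2 runs person-time to the event date), and which calendar month the event belongs to. If the two sentences disagree, the programmer has to choose between them, and the choice affects incidence rates and vaccine efficacy for this endpoint.

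No other rule settles the matter. The PP Set for Efficacy (Section 5.7) and the mITT1 Set (Section 5.6) require negative status at baseline but do not remove participants infected between dose 1 and 14 days after dose 2. The Appendix B visit windows are written for safety and immunogenicity, not efficacy.

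**Working it through.** The plan gives no figure to reproduce. The check applies the written rules to constructed timelines, which are illustrations and not trial data.

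**Inputs**

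- Dose days (Part 1A SAP, 4.1.1.1): "Each participant will receive one injection of mRNA-1273 or placebo on Day 1 and Day 29".
- Window test (Part 1A SAP, 6.5.1.1): "Cases will be counted starting 14 days after the second injection, i.e. date of documented infection" minus the date of the second injection must be at least 14. Section 6.5.1.2 gives the window in words only, so using the same subtraction there is an assumption. With dose 2 on Day 29 the window opens on Day 29 + 14 = Day 43.
- Date as written: the earlier of positive serology and positive scheduled RT-PCR.
- Alternative date: the earliest test that qualifies under the case rule, at any visit.

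**Results** (days after dose 2 = date − 29)

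| Assumed timeline | Date as written | Days after dose 2 | Counted | Earliest qualifying test | Days after dose 2 | Counted |
|---|---|---|---|---|---|---|
| A. Unscheduled PCR+ Day 100 only | none | – | cannot be decided | Day 100 | 71 | yes |
| B. Unscheduled PCR+ Day 20, serology+ Day 57 | Day 57 | 28 | yes | Day 20 | −9 | no |
| C. Unscheduled PCR+ Day 35, serology+ Day 57 | Day 57 | 28 | yes | Day 35 | 6 | no |
| D. Unscheduled PCR+ Day 42, serology+ Day 57 | Day 57 | 28 | yes | Day 42 | 13 | no |
| E. Unscheduled PCR+ Day 43, serology+ Day 57 | Day 57 | 28 | yes | Day 43 | 14 | yes |
| F. Unscheduled PCR+ Day 100, serology+ Day 209 | Day 209 | 180 | yes | Day 100 | 71 | yes |
| G. Scheduled PCR+ Day 29, serology+ Day 57 | Day 29 | 0 | no | Day 29 | 0 | no |

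**Reading the table**

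- A has no date under the date sentence, so its window status and person-time are undefined.
- B, C and D have a first positive test before Day 43 but are counted, because the serology date replaces it.
- F stays in the window but is dated 209 − 100 = 109 days late, which adds person-time and moves the calendar month.
- G is the control. A pre-window positive at a scheduled swab is handled the same way under both rules, so the shift comes only from the scheduled-visit limit.

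The pattern does not depend on dose 2 being on time. If dose 2 slips to Day 50 (the extension of 21 days in Appendix E, note 3, with later visits rescheduled), the window opens on Day 64 and the serology visit falls on Day 78, still after the window opens.

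**Component against composite (Part 1A SAP, 6.5.1.1)**

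For timeline C, two parts of 6.5.1.1 point in different directions. The earlier-date rule and the 14-day subtraction date the infection at Day 35 and leave it out. The sentence before Table 2 and the second row of Table 2 accept a positive serology at Day 57 or later as sufficient, which would count it. The section does not say which governs.

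**The case against.** **Unscheduled swabs may rarely come from symptom-free participants.** The illness-visit swab in Appendix E, note 11, follows suspicion of COVID-19, and Table 2 of the Part 1A SAP names only scheduled and symptom-prompted swabs. Exposure-prompted swabs appear only in Table 1 of the second SAP. This stands as a limit on size. It does not remove the inconsistency, because the SAP itself lists unscheduled and illness-visit positives as a route to an asymptomatic case.

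**The time formula may supply the missing date.** It refers to the date of the infection test, which a programmer could take as the date of the positive swab. That is a reasonable reading, so a reader who infers that timeline A is certain to be lost goes too far. But the test is not defined, and the reading contradicts the date sentence just above it.

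**Asymptomatic cases outside the composite.** A reader might infer that timelines B to D prove that a counted asymptomatic case can be missing from the overall infection count. The document does not establish this, because the serology route in 6.5.1.1 can be read to include them.

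**A 152-day stretch without scheduled RT-PCR.** A reader might take Day 57 to Day 209 (209 − 57 = 152 days) as a period in which unscheduled swabs are the only RT-PCR source. That gap is nominal. Appendix E allows the Day 209 visit 56 days early, so a scheduled swab can occur from Day 153, which is 96 days after Day 57. A convalescent-visit swab is also planned after diagnosis.

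**Low stakes.** No success criterion rests on this endpoint, and cases are also summarised from 14 days after dose 1, where timelines B and C count under either date. This is correct and bounds the importance of the point.

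**Conclusion.** The case rule and the date rule in Section 6.5.1.2 do not match, in either SAP. Under the date sentence, a case known only from an unscheduled RT-PCR has no documented date. A case with an unscheduled RT-PCR and later seroconversion is dated at the serology, which lengthens person-time and can bring a first positive before Day 43 into the post-dose-2 window. Whether such a participant also enters the composite in the Part 1A SAP is unclear.

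The conclusion on window placement assumes that the 14-day subtraction stated for the sister endpoints also applies here. How many participants are affected cannot be worked out from the document, and the number may be small. The endpoint is secondary in Part 1A and exploratory in the second SAP. The correction is worth making, but the primary immunobridging conclusion does not depend on it.

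**What to change.** In Section 6.5.1.2 of both SAPs, replace the date sentence. The case date should be that of the earliest test that qualifies under the case rule: a positive post-baseline RT-PCR at any scheduled, unscheduled or illness visit, or a positive nucleocapsid serology, in each case with absence of symptoms. Apply the 14-day test explicitly to that date, and use the same date in the time formula and for person-time.

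In Section 6.5.1.1, state that the same earliest-date rule governs when an early RT-PCR is followed by seroconversion at Day 57, so that the component and the composite agree. Copying the 6.5.1.1 date rule across without this statement would carry its own ambiguity into a second endpoint.

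Restricting the case rule to scheduled visits would also be consistent, but it would discard cases that the plan now accepts.

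The cost is a sentence or two in each SAP and a re-run of the derivation. A few cases may move out of the post-dose-2 count.

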### 6.5.1.3.Derivation of COVID-19

This is a secondary efficacy endpoint: the incidence of the first occurrence of COVID-19 starting 14 days after the second dose of IP. COVID-19 is defined as symptomatic disease based on the criteria specified in [Section 3.2](#). Cases are defined as participants meeting clinical criteria based on both symptoms for COVID-19 and positive RT-PCR test results.

Surveillance for COVID-19 symptoms will be conducted via biweekly telephone calls or eDiary. Subjects reporting COVID-19 symptoms, as defined in [Section 7.3.2 of the protocol](#), will be arranged an illness visit to collect an NP swab.

For this efficacy endpoint, a COVID-19 case will be identified as a positive post-baseline RT-PCR test result, together with eligible symptoms, i.e. a positive PCR result of the eligible symptoms summarized below in Table 3.

**Table 3. Derivation for COVID-19 (P301 primary case definition)**

	COVID-19
Post-baseline PCR result	Positive, AND
Systemic Symptoms	at least TWO of the following systemic symptoms : Fever ( $\geq 38^{\circ}\text{C}/\geq 100.4^{\circ}\text{F}$ ), chills, myalgia, headache, sore throat, new olfactory and taste disorder(s); OR
Respiratory symptoms	at least ONE of the following respiratory signs/symptoms: cough, shortness of breath or difficulty breathing, OR clinical or radiographical evidence of pneumonia.

The date of documented COVID-19 (case) will be the later date of ([2 systemic symptoms reported, or respiratory symptom reported] and, [date of positive PCR test]). Specifically, the date of documented COVID-19 will be the later date of the following two dates (date of positive PCR test, and the date of eligible symptom(s)), and the two dates should be within 14 days of each other.

- Date of positive PCR test,
- Date of eligible symptom(s), defined as earliest of
  - Respiratory symptom: earliest date of an eligible respiratory symptom is reported
  - Systemic symptoms: earliest date of 2 eligible systemic symptom is reported

The time to the first occurrence of COVID-19 will be calculated as:

Time to the 1st occurrence of COVID-19 = Date of documented COVID-19 – Date of randomization + 1.

Cases will be counted starting 14 days after the second injection, i.e. date of documented COVID-19 - Date of the 2nd injection  $\geq$  14.

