#### **6.5.1.4. Derivation of Secondary Case Definition (CDC case definition) of COVID-19**

This is a secondary efficacy endpoint: the incidence of the first occurrence of COVID-19 cases meeting the secondary case definition, starting 14 days after the first dose of IP, and COVID-19 cases starting 14 days after the second dose of IP.

The secondary case definition of COVID-19 is defined by the following criteria:

- One systemic or respiratory symptoms: fever (temperature  $> 38^{\circ}\text{C}/\geq 100.4^{\circ}\text{F}$ ), or chills, cough, shortness of breath or difficulty breathing, fatigue, muscle aches, or body aches, headache, new loss of taste or smell, sore throat, congestion or runny nose, nausea, or vomiting or diarrhea, AND
- At least one positive RT-PCR test for SARS CoV-2

Date of the documented secondary definition of COVID-19 will be later date of:

- Date of the positive RT-PCR test (prompt by symptom)
- Date of eligible symptom for secondary definition of COVID-19, defined as the earliest date of first eligible symptom is reported

and the two dates should be within 14 days of each other.

Secondary case definition of COVID-19 cases will also be summarized based on tests performed after randomization, and based on tests performed at least 14 days after first dose of IP.

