**Table 2. Derivation for COVID-19**

	COVID-19
Post-baseline PCR result	Positive, AND
Systemic Symptoms	at least TWO of the following systemic symptoms : Fever ( $\geq 38^{\circ}\text{C}/\geq 100.4^{\circ}\text{F}$ ), chills, myalgia, headache, sore throat, new olfactory and taste disorder(s); OR
Respiratory symptoms	at least ONE of the following respiratory signs/symptoms: cough, shortness of breath or difficulty breathing, OR clinical or radiographical evidence of pneumonia.

The date of documented COVID-19 (case) will be the later date of ([2 systemic symptoms reported, or respiratory symptom reported] and, [date of positive PCR test]). Specifically, the date of documented COVID-19 will be the later date of the following two dates (date of positive PCR test, and the date of eligible symptom(s)), and the two dates should be within 14 days of each other.

- Date of positive PCR test,
- Date of eligible symptom(s), defined as earliest of
  - Respiratory symptom: earliest date of an eligible respiratory symptom is reported
  - Systemic symptoms: earliest date of 2 eligible systemic symptom is reported

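### The COVID-19 case rules take the earliest eligible symptom report without tying it to the PCR-positive illness, so applied as written they drop a true case that follows an earlier qualifying report

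*SAP*

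**What the plan says.** SAP for Part 1A, Section 6.5.1.3, makes a case from a positive post-baseline RT-PCR plus eligible symptoms. Under Table 3 the symptom date is the earlier of two dates ("Date of eligible symptom(s), defined as earliest of"): the respiratory date ("Respiratory symptom: earliest date of an eligible respiratory symptom is reported") and the systemic date, on which two eligible systemic symptoms are reported. The case date is the later of the symptom date and the PCR date, "and the two dates should be within 14 days of each other". Counting is restricted through the case date: "Cases will be counted starting 14 days after the second injection, i.e. date of documented COVID-19" less the second injection date must be at least 14 days.

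Section 6.5.1.4 gives the CDC definition the same structure. One listed symptom suffices, its date is "defined as the earliest date of first eligible symptom is reported", and the same 14-day condition follows. Here the RT-PCR is described as prompted by symptoms.

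The SAP for Parts 1B, 1C, 2 and 3 repeats both rules in its Sections 6.5.1.3 and 6.5.1.4. Its Table 2 reads "Systemic symptoms: earliest date of 2 eligible systemic symptom is reported".

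Section 6.5.1.3 also states that "Surveillance for COVID-19 symptoms will be conducted via biweekly telephone calls or eDiary", so one participant can contribute many symptom reports.

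**The concern.** The order of operations is the problem. A single symptom date per participant is fixed first, and the 14-day check is applied to that date alone. If it belongs to an earlier, unrelated illness, it fails the check, and nothing in the text tells the programmer to try the next report. The PCR must be post-baseline, but no start or end is set for the symptom search, and the counting rule after dose 2 acts on the case date and not on that search.

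Earlier unrelated illness is foreseeable: follow-up runs for months, and footnote 11 of Appendix E (SAP for Part 1A) has illness-visit swabs tested for other respiratory pathogens. At stake are the COVID-19 case counts under both definitions, the incidence rates by group, time period and calendar month (Section 6.5.2), and the precision of VE in Part 1A. Section 1 of each SAP says that the SAP prevails over the protocol on methods, so its wording carries weight.

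**Working it through.** The documents state no figure for this rule, so there is none to reproduce. The check has two parts.

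**1. The rule on test timelines.** Inputs from Table 3: one respiratory symptom or two systemic symptoms qualify; the earlier date is used; the window is 14 days. In every timeline the true illness is a cough on Day 150 with a positive PCR on Day 151. *As written* takes the earliest qualifying report and then applies the window. *Anchored* searches only within 14 days of the PCR.

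| Earlier report | Gap to PCR (days) | As written | Anchored |
|---|---|---|---|
| none | – | case, Day 151 | case, Day 151 |
| cough, Day 80 | 151 − 80 = 71 | lost | case, Day 151 |
| two systemic symptoms, Day 80 | 71 | lost | case, Day 151 |
| one systemic symptom, Day 80 | 71 | case, Day 151 | case, Day 151 |
| runny nose (not in Table 3), Day 80 | 71 | case, Day 151 | case, Day 151 |
| cough, Day 140 | 151 − 140 = 11 | case, Day 151 | case, Day 151 |

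The rule as written loses two of the six timelines and the anchored rule loses none. Under the CDC definition read the same way, a runny nose or one listed systemic symptom such as headache on Day 80 would also be enough to lose the case.

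**2. Possible size.** The documents give no rate of unrelated qualifying illness, so a rate r per person-year is assumed, constant and independent of the true case, counted from Day 1. With the PCR on day p, the time at risk is T = (p − 14 − 1)/365.25 years, and the share of true cases lost is 1 − exp(−rT).

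Example: p = 120 gives T = 105/365.25 = 0.287; with r = 1 the loss is 1 − exp(−0.287) = 25%.

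| r per year (assumed) | PCR Day 57 | PCR Day 120 | PCR Day 209 |
|---|---|---|---|
| 0.25 | 3% | 7% | 12% |
| 0.5 | 6% | 13% | 23% |
| 1 | 11% | 25% | 41% |
| 2 | 20% | 44% | 65% |

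The loss grows with follow-up, so later periods would show falsely low incidence.

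**3. Effect on VE.** Write pv and pp for the fractions lost in the vaccine and placebo arms. Ignoring the small change in person-time, observed VE = 1 − (1 − VE)(1 − pv)/(1 − pp). If pv = pp, VE does not change. The standard error of the log rate ratio then grows by roughly 1/√(1 − p); for p = 0.25 this is 1/√0.75 = 1.15.

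**The case against.** The best defence is that the 14-day condition selects the pair of dates jointly and is not a filter applied afterwards. Section 6.5.1.3 speaks of "a positive PCR result of the eligible symptoms summarized below in Table 3" and has a symptom report lead to an illness visit and swab. The endpoint is a first occurrence, which suggests that separate illnesses are evaluated, and the CDC rule describes the PCR as symptom-prompted. Under that reading nothing is lost, and a sensible programmer may adopt it. It does not settle the matter: the phrase about the PCR result sets no period, and the CDC wording qualifies the PCR, while the symptom date stays the earliest report. Two programmers could produce different case counts.

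Four stronger readings are tempting and not supported:

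- A reader might infer that the SAP says to use the earliest symptom ever reported. It does not; it is silent on the search period.
- A reader might infer that any earlier symptom loses the case. Under Table 3 a single systemic symptom, or a qualifying report within 14 days of the PCR, does not.
- A reader might add a headache in one month to a sore throat in another to make two systemic symptoms. That needs a further assumption about how the pair is dated.
- A reader might infer that VE is inflated, because headache, myalgia, fever and chills are also solicited reactions (Section 6.3.2). If 10% of vaccine and 5% of placebo cases were lost, a true VE of 80% would read 1 − 0.20 × 0.90/0.95 = 81%; with 30% and 10% it would read 1 − 0.20 × 0.70/0.90 = 84%. Those inputs are invented, and the SAP nowhere says that solicited reactions enter the COVID-19 symptom data.

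It also stands that a dropped case with a positive PCR from 14 days after dose 2 still counts as SARS-CoV-2 infection in baseline-negative participants (Section 6.5.1.1).

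**Conclusion.** Wrong as written, in both case definitions and both SAPs. The rule fixes an unanchored earliest date before applying the window, so followed to the letter it drops true cases preceded by a qualifying report more than 14 days before the PCR. That the rule can do this follows from the text; that cases were in fact lost is not shown.

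The 7% to 44% range near Day 120 rests entirely on assumed illness rates and on literal programming. Equal loss would leave VE unchanged but less precise. It would still bias the incidence rates, including those of the long-term analysis, which Section 6.6 of the SAP for Part 1A summarizes without treatment comparison, so no ratio cancels the loss there.

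**What to change.** In Sections 6.5.1.3 and 6.5.1.4 of both SAPs, reverse the order:

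- For each positive RT-PCR, consider only eligible symptoms reported within 14 days before or after it.
- Under the Table 3 (Part 1A) and Table 2 (other parts) rule, require both systemic symptoms to fall in that window.
- Take the earliest qualifying date within the window as the symptom date.
- Define the case by the first RT-PCR that qualifies, and keep the existing case-date and counting rules.

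The cost is about one sentence per definition and a check of the derivation program. No new data are needed.
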